1.2 Name and Description of Investigational Intervention

Dynamic Supported Mobility (DSM) - The experimental therapy group will receive dynamic weight support (using the ZeroG Gait and Balance training system, Aretech LLC, Ashburn, VA) during all therapy time, and the environment will be arranged to encourage active motor exploration by the child, in order to promote the motor variability, challenge, and error experiences that characterize the typical development of upright motor skills and walking. Activities will be graded in difficulty to the child's ability and will include: moving between the floor and standing, walking, squatting to reach the floor, climbing/walking up and down steps and inclines, and other typical toddler movements, somewhat similar to a play gym for toddlers. The floor area within 3 feet below either side of the overhead track for a distance of approximately 20 feet (approximately 120 ft² total) will be defined with colorful thin rubber interlocking mats and arranged with pediatric toys and activities, tailored to the child's interests and to encourage motor skills just beyond his/her current ability level. The dynamic support system continuously provides a constant amount of weight assistance (as determined by the therapist) by controlling the length of the cable joining the harness and track and by moving along the overhead track as the user moves about the space (i.e. cable lengthens if child moves to the floor and shortens if child climbs up steps, with no lag time). The user's movements are not restricted at all within this space. This arrangement works well to keep children within the limits of the overhead track and provide ample opportunity and space for motor play and exploration. Initial amount of weight assistance will be determined during the first therapy session by the level that allows walking and squatting to reach the floor with the least amount of assistance from the therapist. Weight assistance will be gradually reduced during the treatment phase as postural control and coordination improve. The therapist will minimally assist the child as needed to perform the movements he/she initiates.

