2 STUDY OBJECTIVES

2.1 Primary Objectives (or Aims)

Aim 1. To determine the optimal treatment duration of dynamic supported mobility (DSM) treatment in infants and toddlers with cerebral palsy, between 6 to 24 weeks of treatment.

Hypothesis 1.1. Gross motor ability (measured by the GMFM-66) will exceed individual predicted values in infants and toddlers with cerebral palsy after 12, 18, and 24 weeks of DSM treatment, and gains will be maintained at 3, 6 and 12 month follow-up points.

Hypothesis 1.2. Gross motor function gains will be positively related to the amount of motor error, variability and engagement experienced during DSM treatment.

Aim 2. To determine the futility of dynamic supported mobility compared to conventional rehabilitation in infants and toddlers with cerebral palsy.

Hypothesis 2.1. The frequency of adverse events among participants who receive DSM treatment and those who receive conventional (CONV) treatment will not differ by greater than 10 percent.

Hypothesis 2.2. Participants who receive DSM treatment will demonstrate significantly greater improvements in gross motor ability (measured by the GMFM-66) than participants who receive equal amounts of CONV treatment, and these differences will be maintained at each follow-up point.

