DSM treatment. Children will receive dynamic weight support (ZeroG®, Aretech LLC, Ashburn, VA) during all DSM treatment time. The environment will be arranged to encourage active motor exploration, somewhat similar to a play gym for toddlers, to promote the motor variability, engagement, and error experiences that characterize the typical development of upright motor skills and walking. The floor area within 3 feet below either side of the overhead track for a distance of 20 feet (approximately 120 ft² total) will be defined with colorful thin rubber interlocking mats and arranged with pediatric toys and activities, tailored to the child's interests and to encourage motor skills just beyond his/her current ability. This arrangement worked well in pilot work to keep children within the limits of the overhead track and provide ample opportunity and space for motor play and exploration. Initial amount of weight assistance will be determined by the level that allows walking and squatting to reach the floor with the least amount of assistance from the therapist, up to a maximum of 40% of the child's weight. Greater than 40% weight support produces significant alterations in normal walking biomechanics in healthy adults (unpublished data, communication with system inventor, [name], PhD). Amount of weight assistance will be re-assessed at the start of each session, and will be gradually reduced as postural control and coordination improve to the minimum amount that allows walking and squatting to reach the floor with the least amount of assistance from the therapist. The therapist will minimally assist the child as needed to perform the movements he/she initiates.

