5.2.6 Possible video or photograph

One treatment session will be videotaped each week to quantify participant error experience (number of falls), motor variability (time spent in one motor activity before moving to the next), and salience or motor engagement (time engaged in a dynamic motor activity) during DSM treatment, allowing evaluation of the relationship of these factors to treatment response. The videotaped sessions will also be coded for the amount of time participants spend doing activities in each of the GMFM subscales, to allow evaluation of the relationship between time spent in each activity category and outcome in each subscale. Randomly selected videos will also be used for quality checks to ensure that the two treatments remain different and consistent with the distinguishing characteristics of each group.

Occasional photographs may be taken, if separate consent is provided, for educational or scientific purposes, or as souvenirs for the children.

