6.2.2 Efficacy Analysis

For the analysis of Aim 1, Hypothesis 1.1 (*Gross motor ability will exceed predicted values after DSM treatment and gains will be maintained at follow-up*), GMFCS percentile ranks will be obtained after 6, 12, 18 and 24 weeks of treatment based on actual GMFM-66

scores and age, and will be compared to predicted percentile ranks based on age and initial GMFM-66 score. Mean values and 95% confidence intervals will be calculated for actual and predicted scores. Optimal treatment duration will be identified as the maximum change observed at the related time point which is maintained during the following period. If maximum change occurs after 24 weeks, this time will be considered the optimal duration. Spearman correlation will be utilized to analyze Hypothesis 1.2 (*Outcomes will be related to the amount of error, variability and engagement during treatment*), to estimate the relationship between motor improvement and the amount of motor error, variability and engagement experienced during treatment.

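### Hypothesis 1.2 is tested by an unadjusted Spearman correlation on non-randomised exposures, so starting ability could create or mask the link to treatment response.

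*Combined protocol and SAP*

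**What the plan says.** Hypothesis 1.2 belongs to Aim 1, one of the two primary aims. Section 2.1 words it as: "Gross motor function gains will be positively related to the amount of motor error, variability and engagement experienced during DSM treatment". It therefore concerns the DSM arm alone.

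Section 6.2.2 gives one analysis: "Spearman correlation will be utilized to analyze Hypothesis 1.2", with the purpose "to estimate the relationship between motor improvement and the amount of motor error, variability and engagement experienced during treatment". It names no covariate, partial correlation or stratification, and it does not say on which scale or at which time point improvement is measured.

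The exposures come from coding one videotaped session per week. Section 5.2.6 says this is done to "quantify participant error experience (number of falls), motor variability (time spent in one motor activity before moving to the next", plus time in dynamic motor activity as engagement, "allowing evaluation of the relationship of these factors to treatment response".

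The other two GMFM-66 analyses do take account of where the child starts. For Hypothesis 1.1, section 6.2.2 predicts each child's percentile rank from age and initial GMFM-66 score. For Hypothesis 2.2, it adjusts the arm comparison for baseline score, cognition and caregiver self-efficacy.

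**The concern.** Randomisation protects the comparison of DSM with CONV. It does not protect a comparison of DSM children who fell often with DSM children who fell seldom. How much a child falls, changes activity or keeps moving may depend on how able and how old the child already is. Section 1.2 says "Activities will be graded in difficulty to the child's ability", and section 3.1.2 sets the weight support child by child. Age at entry runs from 12 to 36 months. Expected motor level depends on age and initial score in the plan's own Hypothesis 1.1 prediction.

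If both exposure and gain depend on starting ability, the two can correlate with no direct link between them, or a real link can be hidden. Error, variability and salience are the design rationale for DSM in section 1.3, so a positive rho would naturally be taken as support for those ingredients. Baseline ability could be part of the explanation, and the planned analysis could not show it.

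**Working it through.** **The plan's own figure.** The only precision statement is in section 6.3: a 95% confidence interval of +/- 6 for the arm difference with 17 per arm and SD 9. It reproduces: 1.96 x 9 x sqrt(2/17) = 6.05. It concerns the arm comparison; no precision is given for Hypothesis 1.2.

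**Inputs from the documents.** There are 17 children per arm after attrition and 21 assigned per arm (section 6.3). The level is two-sided 0.05, stated in the Aim 2 paragraph of section 6.2.2. Taping needs separate consent (section 3.1.2), so the number for Hypothesis 1.2 may be lower.

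**Inputs assumed.** The documents give no correlation of any exposure with baseline ability or of gain with baseline ability, so a range is shown.

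**Model.** Let Z be baseline ability. Exposure is X = aZ + sqrt(1 - a^2) e1 and gain is Y = bZ + sqrt(1 - b^2) e2, with independent normal errors. X has no effect on Y. The correlation induced between them is a x b; for example 0.5 x 0.5 = 0.25, which is about 0.23 on the rank scale.

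**Tests.**
- Plain Spearman: t = r sqrt((n - 2)/(1 - r^2)).
- Partial Spearman given Z: r_p = (r_XY - r_XZ r_YZ) / sqrt((1 - r_XZ^2)(1 - r_YZ^2)), with n - 3 degrees of freedom.

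**Results**, 40,000 simulated trials per setting:

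| a (exposure) | b (gain) | Mean plain rho | Plain significant, n=17 | Plain significant, n=21 | Partial significant, either n |
|---|---|---|---|---|---|
| 0.3 | 0.3 | 0.08 | 6-7% | 6-7% | 5% |
| 0.4 | 0.4 | 0.15 | 9% | 10% | 5% |
| 0.5 | 0.5 | 0.23 | 15% | 18% | 5% |
| 0.6 | 0.6 | 0.33 | 27% | 33% | 5-6% |
| 0.5 | 0.3 | 0.14 | 8% | 9-10% | 5% |
| 0.5 | 0.2 | 0.09 | 7% | 7% | 5% |
| -0.5 | 0.5 | -0.23 | 15% | 18% | 5% |

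In the last row, significant results in the hypothesised positive direction occur in only 0.2-0.3% of trials. A larger sample does not help the plain test: at a = b = 0.5 and n = 30 it is significant in 24%.

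**Cost of adjustment.** The critical |rho| is t / sqrt(df + t^2), with df = n - 2 unadjusted and n - 4 after adjusting for baseline and age.
- n = 17: 2.131 / sqrt(15 + 2.131^2) = 0.48 becomes 2.160 / sqrt(13 + 2.160^2) = 0.51.
- n = 21: 2.093 / sqrt(19 + 2.093^2) = 0.43 becomes 2.110 / sqrt(17 + 2.110^2) = 0.46.

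At rho = 0.3 and n = 21, the Fisher-z interval with variance (1 + rho^2/2)/(n - 3) runs from -0.16 to 0.65. With n - 5 in place of n - 3, for two covariates, it runs from -0.19 to 0.67.

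**Limit of adjustment.** Suppose exposure also correlates 0.3 with the part of gain that baseline does not explain, because improvement during treatment changes exposure (a = b = 0.5 otherwise). The baseline-adjusted test is then significant in 25% (n = 17) or 31% (n = 21) of trials.

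**The case against.** A reader might infer that the test fails its 5% level. The documents do not support that. Hypothesis 1.2 is worded as an association, and section 6.2.2 speaks of estimating a relationship. For that null hypothesis plain Spearman holds about 5%. The rates above arise only when the question becomes whether exposure and gain are linked beyond starting ability. Section 6.3 also says the study was sized for estimates and confidence intervals. This objection stands and limits the point to interpretation.

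The size and sign of any bias are assumed; this also stands. Individual grading of activities and support might weaken the tie between ability and exposure as easily as strengthen it. Eligibility narrows ability too: children must begin to pull to stand, and independent walkers are excluded. At correlations of 0.3 the effect is small. If abler children fall less but gain more, the bias works against the hypothesis.

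The outcome may already be adjusted. If improvement means actual minus predicted percentile rank, as in Hypothesis 1.1, age and initial score are largely handled. But section 6.1 makes change in GMFM the primary endpoint and Hypothesis 1.2 speaks of gains, so raw change is the more natural reading. The plan should say which is meant.

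The analogy with Hypothesis 2.2 is partial. The plan gives no reason for its baseline adjustment there, and age is not among those covariates. The case for age rests on the Hypothesis 1.1 prediction.

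Finally, adjustment is no cure. Weight support "will be gradually reduced as postural control and coordination improve", and exposure is recorded throughout treatment, so improvement may drive exposure. Partial Spearman returns to about 5% in the table only because baseline is there the sole common cause.

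**Conclusion.** The point holds as a cheap improvement. The only planned analysis of Hypothesis 1.2 is unadjusted, uses non-randomised exposures within one arm, and leaves out two variables that the plan itself uses to predict motor level. If improvement is raw GMFM-66 change, starting ability could create or mask a correlation. With no direct link, the chance of a significant plain result ranges from about 6-7% at assumed shared correlations of 0.3 to 27-33% at 0.6, for 17 to 21 children. These correlations are assumptions, and the documents settle neither their size nor their sign.

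It would go too far to conclude that a positive rho in this trial must be spurious, or that an adjusted rho would establish an active ingredient. The documents support neither. The randomised comparison in Hypothesis 2.2 is unaffected, as are Hypothesis 1.1 and the safety analysis.

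**What to change.** In section 6.2.2, for Hypothesis 1.2:

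1. State that improvement is the change in GMFM-66 from baseline to one named time point.
2. Make the main estimate for each exposure a partial Spearman correlation adjusting for baseline GMFM-66 and age, with a 95% confidence interval.
3. Show the unadjusted rho beside it as descriptive.
4. Describe the result as associational, and say that adjustment does not remove the influence of improvement on exposure during treatment.

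This should be fixed before the data are analysed, so that the choice cannot follow the results. Both covariates are already collected, and in SAS a PARTIAL statement in PROC CORR SPEARMAN fits the analysis. The price is two degrees of freedom: the critical |rho| rises from about 0.48 to 0.51 at n = 17 and from 0.43 to 0.46 at n = 21. Estimates will be imprecise with or without the change.

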4.2 Treatment Phase

4.2.1 Assessment sessions 1-5

- Randomization (Assessment 1 only)
- Weight
- Gross motor function (GMFM-66)
- Secondary outcomes (Postural control, physical activity, caregiver satisfaction, Child Engagement in Daily Life)
- BSID-III, cognitive scale (Assessments 1 and 5)
- Family Empowerment Scale (Assessments 1 and 5)
- Possible video or photograph

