5.2.4 Bayley Scales of Infant and Toddler Development, cognitive scale

The cognition age equivalent obtained from the BSID-III will be used as a covariate as patient cognition is known to influence response to rehabilitation.^{56,57} To avoid a learning effect from repeated testing, this will be completed only every 6 months.

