5.2.5 Family Empowerment Scale

One caregiver of each participant will complete the Family Empowerment Scale to obtain a measure of the caregiver's self-efficacy, also known to influence response to

rehabilitation.⁵⁸ To avoid caregivers remembering their prior responses, this will be completed only every 6 months.

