To address Aim 2, Hypothesis 2.2 (*Participants who receive DSM treatment will demonstrate greater improvements than participants who receive CONV treatment, and the differences will be maintained at follow-up*) will be analyzed by comparing GMFM-66 outcomes between participants receiving DSM treatment and those receiving CONV treatment. Baseline characteristics in each group will be compared using two-sample tests, including t-tests, the Mann-Whitney test, and chi-square tests, as appropriate for the respective type of data. We will then use a univariate approach for comparing the two treatments using analyses of variance and covariance (ANCOVA). Measurements at 6, 12, 18 and 24 weeks, as well as at both follow-up points after treatment will be individually compared between the two treatment conditions using baseline score, cognition and caregiver self-efficacy as covariates. We will also use a multivariate approach using linear mixed effects model⁵⁹ or the Generalized Estimating Equation (GEE).⁶⁰ The advantage of using the mixed effects model or the GEE approach is that they will not drop subjects from the analysis due to not having measurement at any of the post-treatment time points. Also, such analyses will allow us to examine the between subjects effects which represent a factor with two levels (treatment conditions) and within subjects effects which represent time effects (pre and post measurements) and a time by condition interaction. The random effect model will be implemented utilizing SAS Proc Mixed and the GEE will be implemented by SAS Proc Genmod. (SAS/STAT User's Guide, 2004, Version 9. Cary, NC: SAS Institute, Inc). Cognition and caregiver self-efficacy will be included as covariates in these analyses. Two-sided p values of less than 0.05 will be considered statistically significant. Similar procedures will be used for the analysis of secondary outcomes, with appropriate tests for parametric (postural control, physical activity) and non-parametric measures (caregiver satisfaction, Child Engagement in Daily Life).

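### Entered as baseline main effects, cognition and caregiver self-efficacy leave the time-by-condition estimate of the mixed model or GEE essentially unadjusted

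*Combined protocol and SAP*

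**What the plan says.** Section 6.2.2 (Efficacy Analysis) plans two analyses of GMFM-66 for Hypothesis 2.2.

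- **Per-visit ANCOVA.** Each post-baseline measurement is "individually compared between the two treatment conditions using baseline score, cognition and caregiver self-efficacy as covariates".
- **Mixed model or GEE.** Condition is the between-subjects factor. The model also has "within subjects effects which represent time effects (pre and post measurements) and a time by condition interaction", so the pre-treatment score is a level of the time factor and therefore a response. The covariates get one sentence: "Cognition and caregiver self-efficacy will be included as covariates in these analyses". Baseline GMFM-66 is not named as a covariate here, and no covariate-by-time term is given.

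The reason for adjusting is given in section 5. Cognition is to be "used as a covariate as patient cognition is known to influence response to rehabilitation" (5.2.4), and the Family Empowerment Scale supplies "a measure of the caregiver's self-efficacy, also known to influence response to" rehabilitation (5.2.5).

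During treatment the schedule has "BSID-III, cognitive scale (Assessments 1 and 5") and "Family Empowerment Scale (Assessments 1 and 5") (section 4.2.1). In follow-up both measures are taken at 6 and 12 months (section 4.3.1). The plan does not say which of these values is the covariate.

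**The concern.** Section 6.1 defines the primary endpoint as change from baseline, and both covariates are justified by their influence on response, which is the change. In a model with the pre-treatment score as a response, the between-group difference in change is the time-by-condition contrast. A child-level covariate with a single coefficient moves the pre-treatment and later scores by the same amount, so it explains level and not change.

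An analysis reported as adjusted for cognition and self-efficacy would then give an effectively unadjusted DSM–CONV difference in change. Section 6.3 sizes the trial to deliver estimates and confidence intervals, so unused precision is a real cost. These are also the models chosen because they retain children with missing visits, and that is where an adjustment for predictors of response could matter.

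**Working it through.** **The plan's own figure.** Section 6.3 gives 17 per arm, SD 9 and a half-width of 6. With the normal quantile, 1.96 × 9 × √(2/17) = 6.05. With t on 32 df, 2.037 × 9 × √(2/17) = 6.29. The figure is reproduced, and it assumes no covariate adjustment.

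**Algebra.** Let the model have a mean for each group g and visit t, plus β·x for a baseline covariate x. With complete data the fitted mean is ȳ(g,t) − β·x̄(g), apart from a term common to both groups. The change from visit 0 to visit t in group g is [ȳ(g,t) − β·x̄(g)] − [ȳ(g,0) − β·x̄(g)] = ȳ(g,t) − ȳ(g,0). The covariate is gone, whatever the working covariance.

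**Numerical check.** The documents give no covariate effects, so the generating values are assumptions: 21 per arm, 8 visits, and two standardised covariates acting on both level and slope. At week 24 they account for 8.32 of a gain variance of 31.06 (8.32 + 10.24 random slope + 12.5 residual), or 27%, which is a strong effect.

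Complete data, week-24 time-by-condition effect (SE):

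| Model | No covariates | Main effects | Covariate by visit |
|---|---|---|---|
| REML random intercept | 4.055 (1.454) | 4.055 (1.454) | 4.226 (1.379) |
| GEE, exchangeable | 4.055 (1.493) | 4.055 (1.493) | 4.226 (1.439) |

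In a second data set with a built-in imbalance, the estimate was 5.491137 with and without main effects under compound symmetry, random-slope, AR(1) and independence covariances. It moved to 5.179869 only with covariate-by-visit terms.

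About 20% dropout by week 24, 1,000 simulated trials per mechanism (none / main effects / by visit):

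- Random dropout: main effects shifted the estimate by 0.03 on average, at most 0.23. Empirical SD 1.90 / 1.90 / 1.66.
- Dropout depending on covariate and arm, a deliberately strong mechanism: bias 0.71 / 0.66 / −0.04, with Monte Carlo error about 1.83/√1000 = 0.06.

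**What remains adjusted.** In the REML fit the SE of the condition main effect fell from 2.474 to 2.251 with the covariates. In the week-24 ANCOVA the SE fell from 1.546 to 1.437.

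**Visit-specific values.** The eight visits are baseline, weeks 6, 12, 18 and 24, and months 3, 6 and 12. The covariates are scheduled at baseline, week 24 and months 6 and 12, so 4 of 8 visits have none. In a simulated fit with a time-varying covariate available at every visit, the estimate went from 4.055 to 4.090 (mixed model) or 4.107 (GEE). Such values do not cancel, but those after baseline are post-randomisation.

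**Precision at stake, 17 per arm, SD 9.** With two covariates explaining a share R² of the gain variance, the expected variance multiplier is (1 − R²) × 31/29. The second factor is 1 + 2/(34 − 2 − 3), the average cost of estimating two normally distributed covariates.

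| Assumed R² | Multiplier | Half-width, normal quantile | Half-width, t on 30 df |
|---|---|---|---|
| 10% | 0.962 | 5.93 | 6.18 |
| 20% | 0.855 | 5.60 | 5.83 |
| 30% | 0.748 | 5.23 | 5.45 |

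Simulated average half-widths agree: from 6.1–6.2 unadjusted to 6.0–6.1, 5.6–5.8 and 5.2–5.4. At R² = 0 the interval widens by √(31/29) − 1 = 3.4%, or 3.7% with the change in t quantile. Break-even is near 1 − 29/31 = 6.5%.

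**The case against.** The strongest reply is that the text is under-specified rather than wrong. It does not say main effects only, it does not call the interaction the sole treatment estimate, and section 6.1 would allow change itself to be the response, in which case plain covariates would adjust it. That last reading sits badly with a time factor that includes the pre-treatment measurement. An analyst who follows section 6.2.2 literally with baseline covariate values obtains the unadjusted contrast, so the wording still needs fixing.

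Other parts of the reply stand, and they rule out stronger conclusions that a reader might draw:

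- **That the covariates adjust nothing.** Cancellation is exact only for baseline values and complete data. The condition main effect is adjusted, and a trace of adjustment remains under dropout.
- **That the DSM–CONV comparison as a whole is unadjusted.** The per-visit ANCOVA uses baseline score and both covariates, and nothing in section 6.2.2 ranks the repeated-measures models above it.
- **That chance imbalance biases the result.** For a covariate correlated 0.3 with gain, a typical imbalance corresponds to √(2/17) × 0.3 × 9 = 0.93 points. Under randomisation with complete data this is random variation already inside the standard error. It is not bias.
- **That half the visits will be lost.** Records at weeks 6, 12, 18 and month 3 would leave the fit only if visit-specific values were used and nothing was carried forward or imputed. The plan does not say so; its gap is that the choice is unstated.

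**Conclusion.** The point holds for the time-by-condition estimate in the mixed model or GEE, and only there. With baseline covariate values that estimate is unadjusted with complete data and effectively unadjusted at the anticipated 20% attrition, although the protocol says both factors influence response. The alternative of visit-specific values is unsatisfactory for a different reason: half the visits have no value and the later ones follow randomisation.

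The main consequence is lost precision. Its size rests on an assumed covariate strength that the documents do not give: almost nothing at 10% of the variance in gain, and roughly 13–14% of the half-width at 30% (1 − √0.748 = 13.5%). Bias is possible if dropout depends on the covariates and on arm; the 0.7 points seen in simulation belongs to a deliberately strong mechanism. The sample-size calculation is unaffected. This is a cheap improvement, not a threat to the trial's conclusions.

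**What to change.** State in section 6.2.2 that the Assessment 1 values of cognition and caregiver self-efficacy are the covariates in all GMFM-66 models, and that later values are not used as covariates. Then choose one of two forms for the mixed model or GEE:

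- (a) keep the pre-treatment score as a response and include each covariate's interaction with visit; or
- (b) use only post-baseline GMFM-66 scores as responses, with baseline GMFM-66, cognition and self-efficacy as covariates. This matches the ANCOVA already planned.

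The change is a sentence or two of SAP text, with no new data. Form (a) adds two coefficients at each of seven post-baseline visits, 14 in all, which is noticeable with 34 to 42 children; form (b) can be more economical. If the covariates explain little of the gain, the interval could be up to about 3–4% wider.
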